## Amendment 4 (15-Jun-2017)

### Amendment rationale

As of 15-Jun-2017, 178 patients have been randomized (60 chelation naïve and 118 pre-treated patients). The pre-treatment arm is fully accrued.

The purpose of this amendment is to include an interim analysis, allow for paper PRO completion, and clarify various points to improve site understanding and consistency in implementation of the protocol.

Amendment rationales are as follows:

1. With this amendment, one interim analysis has been added to allow for early analysis of the data if requested by the health authority.
2. To allow for paper PRO questionnaires use in case of technical issue or malfunctioning of the electronic device.
3. To clarify the completion of the ObsPRO questionnaires for patients who turn 10 years will continue to be completed by the caregiver.
4. To clarify the inclusion/exclusion criteria for the optional extension phase.
5. To clarify that when either TBIL or direct bilirubin are increased and  $> 2 \times$  ULN, it always needs to be checked whether there is also an increase of ALT/AST that meets the definition of DILI.
6. To modify the dose modification and exclusion criteria for direct bilirubin to enhance enrolment and reduce the amount of study drug interruptions without compromising safety. Many transfusion-dependent anemia patients have higher baseline level of direct bilirubin due to hemolysis. Implementation of these less strict exclusion and dose modification criteria will not have any impact on capturing patients with Drug induced liver injury as this only occurs in case of increase of direct bilirubin  $> 2 \times$  ULN.
7. To include dose modifications in case of Toxic epidermal necrosis (TEN) on Table 6-2 as per latest IB update.
8. To correct height and weight to monthly in the optional extension phase to align with the CRF and collection requirements.
9. To re-define Safety Set 4. At the end of the study, safety data for the optional extension phase data will be analyzed considering core and extension phases for patients who received granule formulation. The Safety Set 4 will be used and the FAS-4 has been removed.
10. Baseline categories for serum creatinine, creatinine clearance, ALT, AST and urine protein/creatinine ratio have been re-defined to align with the protocol exclusion and dose modification criteria.

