For patients with baseline value $>$ 3.0 -5.0 x ULN	Maintain dose level. Repeat LFTs a as soon as possible, preferably within 48-72 hours from awareness of the abnormal results; if abnormal lab values are confirmed upon the repeat test, then monitor LFTs a , weekly, or more frequently if clinically indicated, until resolved to $\leq$ 5.0 x ULN
> 10.0 - 20.0 x ULN	Omit dose. Repeat LFTs a as soon as possible, preferably within 48-72 hours from awareness of the abnormal results; monitor LFTs a weekly, or more frequently if clinically indicated, until resolved to $\leq$ baseline. Then dose reduction of 5 or 10 mg/kg/day for deferasirox DT and of 3.5 or 7 mg/kg/day for deferasirox granules.
> 20.0 x ULN	Discontinue patient from study drug treatment Repeat LFTs a as soon as possible, preferably within 48-72 hours from awareness of the abnormal results; monitor LFTs a weekly, or more frequently if clinically indicated, until resolved to baseline or stabilization over 4 weeks.
Combined b elevations of AST or ALT and bilirubin (direct (conjugated) and/or total)	
For patients with normal baseline ALT or AST or direct (conjugated) bilirubin value:  AST or ALT $>$ 3.0xULN combined with direct (conjugated) bilirubin $>$ 2.0 x ULN without evidence of cholestasis c OR (Note to study team: If supported by available data) For patients with elevated baseline AST or ALT or direct (conjugated)bilirubin value  [AST or ALT $>$ 2x baseline AND $>$ 3.0 xULN] OR [AST or ALT $>$ 8.0 xULN], whichever is lower, combined with [direct (conjugated) bilirubin $>$ 2x baseline AND $>$ 2.0 xULN]	Permanently discontinue patient from study drug treatment. Repeat as soon as possible, preferably within 48 hours from awareness of the abnormal results, then with weekly monitoring of LFTs a ), or more frequently if clinically indicated, until AST, ALT, or bilirubin have resolved to baseline or stabilization over 4 weeks. Refer to Section 6.3.2 for additional follow-up evaluations as applicable.

Dose modifications for deferasirox	

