For patients with normal baseline ALT or AST or total bilirubin value:  AST or ALT >3.0xULN combined with total bilirubin >2.0xULN without evidence of cholestasis c OR (Note to study team: If supported by available data) For patients with elevated baseline AST or ALT or total bilirubin value  [AST or ALT>2x baseline AND >3.0xULN] OR [AST or ALT>8.0 ULN], whichever is lower, combined with total bilirubin >2x baseline AND >2.0xULN	Permanently discontinue patient from study drug treatment.  Repeat as soon as possible, preferably within 48 hours from awareness of the abnormal results, then with weekly monitoring of LFTs a , or more frequently if clinically indicated until AST, ALT, or bilirubin have resolved to baseline or stabilization over 4 weeks. Refer to Section 6.3.2 for additional follow-up evaluations as applicable.
Hepatic impairment	
Moderate hepatic impairment (Child-Pugh Class B)	The study medication will be interrupted and patient monitored. If liver disease prognosis improves, deferasirox can be reintroduced at 10 mg/kg/day for DT and at 7 mg/kg/day for granules or 50% of previous dose, whichever is less. While monitoring continues, dose may be increased by 5 mg/kg/day for DT and by 3.5 mg/kg/day for granules every 2 weeks, to a maximum of 50% of patient's previous dose if the investigator determines that dose increase is in the best interest of the patient. Study medication must be used with caution in such patients.
In patients who develop severe hepatic impairment (Child-Pugh Class C) during the study	Study medication must be discontinued.
Other dose modifications	
Changes in Serum Ferritin	

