### **6.2.4 Follow up on potential drug-induced liver injury (DILI) cases**

Patients with transaminase increase combined with TBIL increase may be indicative of potential DILI, and should be considered as clinically important events.

The threshold for potential DILI may depend on the patient's baseline AST/ALT and TBIL value; patients meeting any of the following criteria will require further follow-up as outlined below:

- For patients with normal ALT or AST or TBIL value at baseline: AST or ALT  $> 3.0 \times$  ULN combined with TBIL  $> 2.0 \times$  ULN
- For patients with elevated AST or ALT or TBIL value at baseline: [AST or ALT  $> 2 \times$  baseline AND  $> 3.0 \times$  ULN] OR [AST or ALT  $> 8.0 \times$  ULN], whichever is lower, combined with [TBIL  $> 2 \times$  baseline AND  $> 2.0 \times$  ULN]

Medical review needs to ensure that liver test elevations are not caused by cholestasis, defined as ALP elevation  $> 2.0 \times$  ULN with R value  $< 2$  in patients without bone metastasis, or elevation of ALP liver fraction in patients with bone metastasis.

Note: (The R value is calculated by dividing the ALT by the ALP, using multiples of the ULN for both values. It denotes the relative pattern of ALT and/or ALP elevation is due to cholestatic or hepatocellular liver injury).

In the absence of cholestasis, these patients should be immediately discontinued from study drug treatment, and repeat LFT testing as soon as possible, preferably within 48 hours from the awareness of the abnormal results. The evaluation should include laboratory tests, detailed history, physical assessment and the possibility of liver metastasis or new liver lesions, obstructions/compressions, etc.

- Laboratory tests should include ALT, AST, albumin, creatine kinase, total bilirubin, direct and indirect bilirubin, GGT, prothrombin time (PT)/INR and alkaline phosphatase.
- A detailed history, including relevant information, such as review of ethanol, concomitant medications, herbal remedies, supplement consumption, history of any pre-existing liver conditions or risk factors, should be collected.
- Further testing for acute hepatitis A, B, C or E infection and liver imaging (e.g. biliary tract) may be warranted.
- Obtain PK sample, as close as possible to last dose of study drug, if PK analysis is performed in the study.

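### Liver stopping rule (Table 6-2 and section 6.2.4): overlapping baseline groups leave unclear which bilirubin threshold governs a child with mixed baseline values

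*Protocol*

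**What the plan says.** Protocol Table 6-2 has two rows for combined elevations, one using direct and one using total bilirubin. Each row has two branches joined by *or* and a single action cell: permanent discontinuation.

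- **Branch 1** in the direct-bilirubin row is introduced by "For patients with normal baseline ALT or AST or direct (conjugated) bilirubin value". It is met when AST or ALT exceeds 3 × ULN with bilirubin above 2 × ULN and no evidence of cholestasis.
- **Branch 2** is introduced by "For patients with elevated baseline AST or ALT or direct (conjugated)bilirubin value". Its transaminase part is either more than twice baseline and above 3 × ULN, or above 8 × ULN. Its bilirubin part is more than twice baseline and above 2 × ULN. It has no cholestasis exception, and in both rows it is preceded by "Note to study team: If supported by available data".

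Section 6.2.4, on potential drug-induced liver injury, uses total bilirubin and defines its groups in the same way: "For patients with normal ALT or AST or TBIL value at baseline" and "For patients with elevated AST or ALT or TBIL value at baseline". Meeting any one criterion is enough there. Discontinuation is ordered only when cholestasis is absent, under both criteria.

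Footnote b of Table 6-2 sends combined elevations of AST or ALT and direct bilirubin that fall short of the thresholds to the isolated-elevation rows. A general note bases dose changes on the worst preceding toxicity. Both combined rows refer to section 6.3.2 for follow-up, but that section lists prohibited concomitant therapy.

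**The concern.** The two groups look as if they were meant to split patients into those with normal and those with raised baseline values. They do not, because one normal test is enough for the first and one raised test is enough for the second. Any mixed baseline falls in both.

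Mixed baselines are to be expected here. The Amendment 4 rationale says "Many transfusion-dependent anemia patients have higher baseline level of direct bilirubin due to hemolysis". Section 5.3 admits direct bilirubin up to 2 × ULN and sets no limit on total bilirubin.

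The choice of branch decides whether a child stops the drug for good. It also bears on which cases enter the section 6.2.4 work-up, which can end in a serious adverse event report of potential drug-induced liver injury.

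**Working it through.** The plan states no figure to reproduce. The check applies both branches as written, with all values in multiples of ULN. A0 and B0 are baseline transaminase and bilirubin; A and B are the on-study values. The patient values are illustrative.

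- Branch 1 covers A0 ≤ 1 or B0 ≤ 1. It is met if A > 3, B > 2 and there is no cholestasis.
- Branch 2 covers A0 > 1 or B0 > 1. It is met if [(A > 2·A0 and A > 3) or A > 8], and B > 2·B0, and B > 2.

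**1. Overlap.** A0 = 0.8 with B0 = 1.5 is in both groups. So is the reverse pattern, A0 = 2.0 with B0 = 0.8. A0 = B0 = 0.8 is in the first only, and A0 = 2.0 with B0 = 1.5 is in the second only.

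**2. Raised bilirubin, normal transaminases.** Since A0 ≤ 1, 2·A0 is at most 2, so the transaminase part of branch 2 reduces to A > 3. Since B0 > 1, 2·B0 exceeds 2, so its bilirubin part reduces to B > 2·B0. Absent cholestasis, every patient who meets branch 2 therefore already meets branch 1. A grid with A0 = 0.8, B0 from 1.1 to 2.0, A from 0.5 to 20 and B from 0.1 to 10 agrees: 0 of 40,000 points met branch 2 without branch 1.

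**3. Where the branches part.** For this child it is only where A > 3 and 2 < B ≤ 2·B0.

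| Baseline direct bilirubin | Range in which only branch 1 is met |
|---|---|
| 1.1 | above 2.0 to 2.2 |
| 1.5 | above 2.0 to 3.0 |
| 2.0 (highest admitted) | above 2.0 to 4.0 |

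With A = 4 and B0 = 1.5: at B = 1.5 neither branch is met, at 2.5 only branch 1, and at 3.1 both.

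**4. Consequence inside the range.** Take A = 4, B0 = 1.5, B = 2.5. Branch 1 gives permanent discontinuation. If branch 2 is taken as the governing rule, it is not met (it needs more than 2 × 1.5 = 3.0), and footnote b leads to the isolated rows. Direct bilirubin above 2 and up to 3 × ULN means omit the dose, then the same dose if resolved within 14 days and a reduced dose if later. For baselines above 1.5 the range runs past 3.0 × ULN, where the next isolated row applies: omit, then a reduction, or discontinuation if not resolved within 14 days.

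**5. Total bilirubin.** With B0 = 2.5 and unchanged, A = 4 meets branch 1 (2.5 > 2). Branch 2 needs more than 2 × 2.5 = 5.0 and is not met.

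**6. Cholestasis.** With cholestasis, A = 4, B0 = 1.5 and B = 3.5, branch 1 is switched off but branch 2 is met (3.5 > 3.0). Reading B as total bilirubin, Table 6-2 then requires permanent discontinuation, while section 6.2.4 orders it only without cholestasis.

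**7. Reverse pattern.** With A0 = 2.0, B0 = 0.8, A = 4.0 and B = 2.5, branch 1 is met. Branch 2 is not, because it needs A above 2 × 2.0 = 4.0.

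**The case against.** The strongest reply is that the text, read as written, gives one answer. Both branches share one action, they are joined by *or*, section 6.2.4 accepts any one criterion, and the worst-toxicity note points the same way. On that reading a child who meets branch 1 never reaches the isolated rows. This stands as far as it goes: a child who meets both triggers gets one instruction. A reader might infer that such a child receives opposite instructions, and the documents do not support that. But the literal reading leaves the baseline-relative bilirubin threshold without effect, absent cholestasis, for children whom branch 2 names.

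Other replies also have force:

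- The range of disagreement for direct bilirubin is limited, and no frequency can be derived.
- An unchanged direct bilirubin should not by itself complete the bilirubin criterion, because values above 2 × ULN are excluded at screening. That scenario belongs to total bilirubin, whereas the Amendment 4 remark concerns direct bilirubin.
- The serious adverse event report needs confirmation on repeat testing and no alternative cause, so a different reading need not change the count.
- The drafting note does not leave the total-bilirubin version wholly in doubt, because section 6.2.4 states it without the note.

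Two further inferences are tempting. One is that branch 2 means uninterrupted treatment in the direct-bilirubin example; the isolated row says omit the dose. The other is that week-25 ferritin is compromised. Sections 6.2.2 and 7.2.2 provide a ferritin value at the end-of-treatment visit within 7 days of the last dose, and section 10.4.3 carries the last value forward. Nothing shows a difference between arms, and the core phase was complete by 18-Dec-2018, before Amendment 6.

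**Conclusion.** The inconsistency is real but narrower than conflicting orders. For mixed baselines, Table 6-2 and section 6.2.4 do not say which threshold governs. For a child with raised bilirubin and normal transaminases, the rule is either ambiguous between 2 × ULN and twice baseline or, read literally and absent cholestasis, has a baseline-relative bilirubin threshold that never acts. The drafting note, the differing cholestasis exception and the wrong cross-reference are separate faults in the same rows.

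This rests on the wording alone. The ranges follow from the thresholds and the screening limit on direct bilirubin; the patient values are examples. No rate of affected children, extra discontinuations or extra reports can be given. The final-analysis SAP tabulates combined elevations against multiples of ULN without a baseline-relative criterion, so that table does not depend on the reading.

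It should be fixed, as an internal inconsistency, because it governs permanent stopping in a pediatric trial with 67 patients in the extension at Amendment 6. No view is taken on which threshold is clinically right.

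**What to change.** Reconcile both combined-elevation rows of Table 6-2, footnote b and section 6.2.4:

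1. Make the two baseline groups mutually exclusive. State one governing branch for each mixed pattern, including raised bilirubin with normal AST/ALT and the reverse. The sponsor's safety team chooses.
2. Resolve the drafting note in both rows, so that it is plain whether branch 2 is in force.
3. Align the cholestasis exception between Table 6-2 and section 6.2.4.
4. Change the follow-up reference from section 6.3.2 to section 6.2.4.

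The cost is the wording of two table rows, a footnote and two bullets, with no added tests or visits. If extension treatment has ended before the text is settled, the report can state which reading was applied to any discontinuation under these rows.

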> 2 - 3.0 x ULN	Omit dose with weekly monitoring of LFTs a , or more frequently if clinically indicated, until resolved to $\leq$ 2.0 x ULN: If resolved in $\leq$ 14 days, then maintain dose level If resolved in $>$ 14 days, then dose reduction of 5 or 10 mg/kg/day for deferasirox DT and of 3.5 or 7 mg/kg/day for deferasirox granules.
> 3.0 - 10.0 x ULN*	Omit dose with weekly monitoring of LFTs a , or more frequently if clinically indicated, until resolved to $\leq$ 2.0 x ULN: If resolved in $\leq$ 14 days, then dose reduction of 5 or 10 mg/kg/day for deferasirox DT and of 3.5 or 7 mg/kg/day for deferasirox granules. If resolved in $>$ 14 days, then discontinue patient from study drug treatment. The patient needs to be monitored weekly (including LFTs a ), or more frequently if clinically indicated, until direct (conjugated) bilirubin have resolved to baseline or stabilization over 4 weeks.
> 10.0 x ULN*	Discontinue patient from study drug treatment The patient needs to be monitored weekly (including LFTs a ), or more frequently if clinically indicated, until direct (conjugated) bilirubin have resolved to baseline or stabilization over 4 weeks.
Isolated AST or ALT elevation	
> ULN - 3.0 x ULN	Maintain dose level
> 3.0 - 5.0 x ULN For patients with baseline value $\leq$ 3.0 x ULN	Maintain dose level. Repeat LFTs a as soon as possible, preferably within 48-72 hours from awareness of the abnormal results; if abnormal lab values are confirmed upon the repeat test, then monitor LFTs a weekly, or more frequently if clinically indicated, until resolved to $\leq$ 3.0 x ULN
For patients with baseline value $>$ 3.0 -5.0 x ULN	Maintain dose level

Dose modifications for deferasirox	
> 5.0 - 10.0 x ULN For patients with baseline value $\leq$ 3.0 x ULN	Omit dose. Repeat LFTs a as soon as possible, preferably within 48-72 hours from awareness of the abnormal results; monitor LFTs a weekly, or more frequently if clinically indicated, until resolved to $\leq$ 3.0 x ULN If resolved in $\leq$ 14 days, maintain dose level If resolved in $>$ 14 days, then dose reduction of 5 or 10 mg/kg/day for deferasirox DT and of 3.5 or 7 mg/kg/day for deferasirox granules.

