Gastrointestinal issues (including diarrhea, constipation, nausea, vomiting and abdominal pain)	
Some basic recommendations, based on practical experience, can be made to guide physicians in managing patients who experience diarrhea.
 
At the first sign of diarrhea, consider anti-diarrheal medication such as loperamide. Remind the patient to discontinue any laxative preparations or stool softeners they may be taking and to eat small, frequent meals. Determine if the patient is lactose intolerant. Deferasirox DT contains lactose in the formulation so supplemental lactase may benefit the patient; however the deferasirox granules do not contain lactose. Remind the patient to drink 8 to 10 glasses of clear liquid per day. Suggest that the patient take their deferasirox DT with water, not with orange juice or apple juice until the diarrhea resolves.
 
Should the gastrointestinal issues (including diarrhea, constipation, nausea, vomiting and abdominal pain) persist, study drug may be discontinued if the investigator believes it is in the best interest of the patient. Novartis may be contacted by the investigator to discuss dosing options if the investigator so desires.

All dose modifications should be based on the worst preceding toxicity.	
a Core LFTs consist of ALT, AST, GGT, total bilirubin (fractionated [direct and indirect], if direct (conjugated) bilirubin > 2.0 x ULN), and alkaline phosphatase (fractionated [quantification of isoforms], if alkaline phosphatase > 2.0 x ULN.)	
b "Combined" defined as direct (conjugated) bilirubin increase to the defined threshold concurrently with ALT/AST increase to the defined threshold	
If combined elevations of AST or ALT and direct (conjugated) bilirubin do not meet the defined thresholds, please follow the instructions for isolated elevation of direct (conjugated) bilirubin and isolated elevation of AST/ALT, and take a conservative action based on the degree of the elevations (e.g. discontinue treatment at the situation when omit dose is needed for one parameter and discontinue treatment is required for another parameter). After all elevations resolve to the defined thresholds that allow treatment re-initiation, re-start the treatment either at the same dose or at one dose lower if meeting a criterion for dose reduction	

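### Table 6-2 gives conflicting liver instructions: footnote b defines a combined elevation by direct bilirubin only, while the total-bilirubin row it annotates orders a permanent stop

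*Protocol*

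**What the plan says.** All of the conflicting text is in the current Table 6-2 (protocol Section 6.2.1).

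- **Heading.** The block that carries superscript b is for combined "elevations of AST or ALT and bilirubin (direct (conjugated) and/or total".
- **Total-bilirubin row.** For a child with normal baseline values the trigger is "AST or ALT >3.0xULN combined with total bilirubin >2.0xULN without evidence of cholestasis". The action is permanent discontinuation. The row sets no condition on direct bilirubin.
- **Footnote b, first sentence.** A combined elevation is "defined as direct (conjugated) bilirubin increase to the defined threshold concurrently with ALT/AST increase to the defined threshold". Total bilirubin is not mentioned.
- **Footnote b, second sentence.** Elevations of AST or ALT with direct bilirubin that "do not meet the defined thresholds, please follow the instructions for isolated elevation of direct (conjugated) bilirubin and isolated elevation of AST/ALT". The footnote then asks for a conservative choice between those rows and describes restarting treatment once values resolve.
- **General line above the footnotes.** "All dose modifications should be based on the worst preceding toxicity".

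Outside the table, Section 6.2.4 defines potential drug-induced liver injury by total bilirubin and requires immediate discontinuation when there is no cholestasis. Section 7.1.3 makes the laboratory abnormalities of Section 6.2 mandatory reasons to stop. For follow-up evaluations, both combined rows point to Section 6.3.2, which is the list of prohibited concomitant therapy. The work-up is in Section 6.2.4.

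**The concern.** A footnote on a heading normally fixes the meaning of the term it marks. Here it is narrower than the heading and leaves out one of the two rows beneath it. A site that looks up the definition first would conclude that raised transaminases with raised total but not raised direct bilirubin are not a combined elevation, and would move to the isolated rows. Those rows allow dosing to continue or restart in a child who meets the protocol's own criteria for potential drug-induced liver injury.

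The pattern is not contrived. The asterisk note to the same table provides for total bilirubin raised through the indirect component alone. The wrong pointer adds a little to the problem, because it leads away from the section that would correct the reading. It does not alter the stop order itself.

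**Working it through.** The plan gives no figure to reproduce, and no power or error-rate arithmetic applies. The check sets the two routes through Table 6-2 side by side.

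**Case.** Normal baseline values, no cholestasis, total bilirubin above 2 and up to 3xULN, direct bilirubin at or below 2xULN. The upper limit of 3xULN keeps clear of the asterisk note, which has its own rule for total bilirubin above 3xULN from the indirect component. Children with raised baseline values are left out because other thresholds apply to them.

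**Step 1, direct bilirubin under footnote b.** The lowest isolated direct-bilirubin row, above ULN and up to 2xULN, says maintain the dose. Direct bilirubin therefore never asks for more than that in this case.

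**Step 2, AST/ALT under footnote b, compared with the total-bilirubin row.**

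| AST or ALT | Total-bilirubin row | Footnote b route (isolated AST/ALT row) | Agree? |
|---|---|---|---|
| >3 to 5xULN | Permanent stop | "Maintain dose level. Repeat LFTs" | No |
| >5 to 10xULN | Permanent stop | "Omit dose. Repeat LFTs"; same dose if resolved within 14 days, reduced dose if later | No |
| >10 to 20xULN | Permanent stop | Omit until back to baseline or below. "Then dose reduction of 5 or 10 mg/kg/day for deferasirox DT and of 3.5 or 7 mg/kg/day for deferasirox granules" | No |
| >20xULN | Permanent stop | Discontinue | Yes |

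The two routes differ in three of the four bands above 3xULN. This describes table rows; it does not count patients.

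**Step 3, worked example.** ALT 4xULN, total bilirubin 2.5xULN, direct bilirubin 1.5xULN. The total-bilirubin row applies because 4 > 3 and 2.5 > 2, so the drug is stopped for good. Under footnote b, direct bilirubin at 1.5 does not exceed 2, so the elevation is not combined. The isolated rows then give maintain for direct bilirubin and maintain for ALT.

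**Step 4, whether the table resolves this itself.** The conservative-choice instruction selects among the isolated rows. In the >3 to 5xULN band no applicable isolated row asks for more than maintain. In the next two bands the strictest is omit, which is still short of a permanent stop. The line on worst preceding toxicity grades severity and does not say which definition of combined governs.

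**Step 5, which reading is intended.** The heading, the total-bilirubin row and Section 6.2.4 all include total bilirubin. Item 5 of the Amendment 4 rationale, used here for intent only, says the check applies when either total or direct bilirubin is raised. Footnote b is the outlier.

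**The case against.** The strongest reply is that nobody following the protocol sensibly would go wrong. The total-bilirubin row states its own thresholds and orders the stop. Section 6.2.4 repeats the trigger and the action, and Section 7.1.3 makes it mandatory. To keep dosing, a site would have to let a definitional footnote override a printed row that fits the child exactly, and would have to treat a joint rise in transaminases and bilirubin as isolated. The instructions to act conservatively and by worst toxicity also lean towards the stricter row.

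Most of this stands. It limits the weight of the point and rules out the inference a reader might draw that the protocol lacks a stop rule for total bilirubin. It does not remove the conflict, because no line says that the row prevails over the footnote.

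Two further objections also stand. The final SAP's liver summary (Section 2.7.4.2) counts ALT or AST above 3xULN with total bilirubin above 2xULN, but it follows a company reporting guideline and lists no direct bilirubin. It therefore cannot show which wording governed dosing. Timing also matters. Amendment 6 says all patients had completed the core phase by 18-Dec-2018, and the extension lasts at most 5 years. If every child entered the extension by that date, the last possible dose falls at about 18-Dec-2023. The final SAP is dated 21-Feb-2024, so correcting the text had probably ceased to affect any dose by then.

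**Conclusion.** The inconsistency is real and is more than clerical, because a literal reading of footnote b yields a different dosing action from the row it annotates. It should be corrected. Its weight is modest, since the right action is printed in the same table and in Section 6.2.4.

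The conclusion covers the defined child only: normal baseline values, no cholestasis, total bilirubin above 2 and up to 3xULN, direct bilirubin at or below 2xULN, and AST/ALT above 3 and up to 20xULN. It assumes that a site applies footnote b as a definition.

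A reader might infer that children were kept on drug after meeting the stop rule, or that the three conflicting bands measure how often this happened. The documents support neither. They identify no such patient and do not say how often total bilirubin alone was raised. The point has no bearing on the co-primary endpoints, the error rate or the power.

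**What to change.** **Text.**

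1. In both sentences of footnote b, replace direct (conjugated) bilirubin with direct (conjugated) and/or total bilirubin.
2. State that the isolated rows apply only when neither combined row is met.
3. In both combined rows, change the follow-up pointer from Section 6.3.2 to Section 6.2.4.

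These are edits to one footnote and one cross-reference. The intended clinical rule does not change and no new data are needed.

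**Optional look-back.** As dosing had probably ended, the final report could list patients with concurrent ALT or AST above 3xULN and total bilirubin above 2xULN, direct bilirubin at or below 2xULN, and no cholestasis. The listing should cover both arms and both phases, show baseline values, and be linked to the dosing records to see whether treatment continued or restarted.

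This is a small extra listing and cannot be had by filtering the planned liver summary. That summary uses worst post-baseline values, is confined to granule-treated patients (Safety Set 4), and has no direct bilirubin. Two data limits should be expected. The liver row of protocol Table 7-2 names total but not direct bilirubin, so direct values may be absent at some extension visits. Section 2.4.1 of the final SAP also restricts some dose summaries to patients with complete dosing dates, which implies that some dates are incomplete. Patients affected by either limit should be shown as undetermined.
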